## 8. PARTICIPANT IDENTIFICATION

### 8.1. Study Participants

One hundred adults with type 2 diabetes and a  $\text{BMI} \geq 27\text{kg/m}^2$  ( $\geq 30\text{kg/m}^2$  if white ethnicity) will be recruited.

### 8.2. Inclusion Criteria

- Participant is willing and able to give informed consent for participation in the study.
- Male or Female, aged 40 years or above.
- Diagnosed with current type 2 diabetes (i.e. not in remission) in the last 6 years
- $\text{BMI} \text{ of } \geq 27\text{kg/m}^2$  ( $\geq 30\text{kg/m}^2$  if ethnicity recorded as white)

- Has a smartphone or computer with internet access (and the correct operating system requirements to use the intervention programme)
- Are able to complete the eligibility and baseline assessments online
- Would like to make changes to their diet or lifestyle to improve their diabetes control, lose weight, or improve their general health

### **8.3. Exclusion Criteria**

The participant may not enter the study if ANY of the following apply:

- Unable to understand the study materials and interventions
- Currently following a weight loss programme (defined as a structured, prescribed and monitored programme and not a self-directed weight loss attempt)
- Pregnant, breastfeeding, or planning to become pregnant during the course of the study
- History of bariatric surgery, including gastric banding
- Currently using insulin therapy
- Proliferative diabetic retinopathy, or maculopathy.
- Recent myocardial infarction or stroke (<3 months)
- Renal failure (chronic kidney disease stage 4 or 5)
- Current active treatment for cancer (other than skin cancer treated with curative intent by local treatment only)
- Their doctor does not feel they are appropriate to participate for another reason (e.g. active eating disorder diagnosis, significant psychological disturbance)

## **9. PROTOCOL PROCEDURES**

An overview of study procedures is shown in appendix B.

### **9.1. Recruitment**

We aim to recruit 100 participants via their GP practices. Based on a conservative response rate of 10% from similar previous studies, we will approach approximately 1000 eligible individuals from approximately 10 GP practices in England(7). The primary care provider will search their electronic registers for eligible individuals and GPs will screen out those to whom it would be inappropriate to send a letter. The letter from their GP will invite the patient to consider taking part in the study and the patient will be directed to the study website for more information and to access the online Participant Information Sheet. Contact details for the research team will be available for them to contact to discuss the study in more detail and/or ask any questions. Participants wishing to be considered for inclusion in the trial will be directed to the section of the website to complete the initial eligibility assessment. This helps to ensure participants have sufficient IT skills to be able to engage with the intervention.

As part of the initial eligibility assessment participants will be asked to report their height and weight to calculate BMI (these numbers will not be recorded, just whether they meet eligibility criteria or not). If the participant is ineligible a pop-up will explain that they do not meet the eligibility criteria for this study and they will not proceed further and no information will be requested. If they are eligible they will be asked to provide their full name and email via an approved secure platform (the SENTRY programming system, run by the University of Oxford Nuffield Department of Primary Care Health Sciences Clinical Trials Unit, where the information will be stored securely and in compliance with local IG policy) so that the research team can contact them. They will also be asked to create a four-digit access code for the online consent.

## **9.2. Informed Consent**

As detailed above (section 9.2) participants will visit a website to read the Participant Information Sheet online and able to print out if they wish to. The Participant Information and Informed Consent presented to the participants online will detail no less than: the exact nature of the study; what it will involve for the participant; the implications and constraints of the protocol; the known side effects and any risks involved in taking part. It will be clearly stated that the participant is free to withdraw from the study at any time for any reason without prejudice to future care, without affecting their legal rights, and with no obligation to give the reason for withdrawal.

The participant will be allowed as much time as they wish to consider the information and have the opportunity to call the research team, their GP or consult other independent parties to ask any questions before they decide whether they will participate in the study. Following their initial eligibility assessment (section 9.1), eligible participants will be sent an email with a link to the online database where consent is taken. They will log in with their full name and access code given previously at the initial eligibility assessment (section 9.1). They will then agree to each statement of the consent form and then sign the consent form by putting their full name and access code. Once consent has been given, participants will click on a link to the electronic data capture system database which will be activated following their consent, to complete the baseline assessment. Participants will be able to download a copy of the consent form to keep for their records.

## **9.3. Baseline Assessments**

All participants will complete a 2 part baseline assessment, firstly online and then at their GP practice.

### **1. Online:**

Participants will be asked to complete a baseline questionnaire requesting demographic information and their current medication, and the standard questionnaires that will be used in the study (the Problem Areas in Diabetes (PAID) score, the EQ5D (quality of life assessment), and a 24 hour dietary recall questionnaire (“Intake24 dietary assessment tool”, where participants are asked to record all food and drink intake in the last 24 hours). This will also further assess whether people are sufficiently able to complete online trial procedures, and only those who complete the questionnaire will be randomised. Participants will be informed in the Participant Information Sheet that they will only be able to enter the study after completing each individual questionnaire fully in one attempt as the system will not allow them to go back into each

questionnaire to answer the remaining questions later. Overall there are 3 questionnaires for each participant to complete. These should take less than 30 minutes to complete. Patients will be able to fill in the baseline questionnaires and 24 hour dietary recall at any time after completion of the online consent form but before the appointment at their GP practice, as long as they complete each questionnaire in one attempt. Should a participant not complete their questionnaires, reminder emails will be sent at one and two weeks after they received the initial invite to complete the questionnaires.

2. At the GP practice (visit 1)

Having completed the online assessment, participants will be asked (via message on their screen on completing the assessment, and followed up via email) to book the in-person portions of their baseline assessment at their GP practice for measures which cannot be conducted online. At this appointment (with a nurse or healthcare assistant), their height, weight and blood pressure will be measured and recorded, and a blood sample taken for baseline values (HbA1c, lipid profile, liver function tests). Once their practice confirms they have attended this appointment they will be sent a link to the randomisation system.

#### **9.4. Randomisation and blinding**

All eligible participants will be individually randomised to one of two arms: Intervention (12 week, app-based dietary support), or control (usual care; no active additional intervention). The randomisation will be conducted using the Redcap inbuilt randomisation software. This ensures full allocation concealment as information on future allocations is not accessible to the person randomising.

The participants will be aware that they will be randomised to either an app-based support programme or control, therefore no blinding can take place. Due to the nature of the intervention it will not be possible to blind members of the study team to participant allocation. A letter will be provided to the participant's GP to inform them of which group the participant has been allocated to.

#### **9.5. Description of study intervention and comparator**

##### **9.5.1. Intervention group**

Participants randomised to the intervention group will receive an email informing them they have been assigned to the intervention group, and that their contact information (name and email) has been securely passed to the provider, who will contact them to process the programme onboarding and account creation. They will contact the participant with information how to download and access the app-based intervention. Thereafter, any identifiable information required by the programme provider application will be provided by the participant. The intervention involves diet, activity and behaviour change components. It comprises a three-month remote behavioural change programme with mentoring from a registered dietitian or nutritionist (health coach), peer group support, structured education articles and activity tracking technology. These elements are accessed via a smartphone or web-based application. Each participant will also receive a hard copy of an instructional handbook and a recipe book.

Participants randomised to the intervention group will also receive 1 additional telephone appointment with their GP or practice nurse, towards the start of the 12 week intervention period, to review their current medications and assess any changes to their medication regime may be warranted in view of their anticipated participation in the programme and planned weight loss. We will provide clinicians with current best practice guidelines they may wish to consider but the decisions for individual patients will remain with their clinician.

For participants in the intervention group, data on participant engagement with the app will be received from the company under appropriate agreements. These data will include (as examples) measures of engagement with the three main components of the programme: Learn, Track, and Support. “Learn” interactions are defined as the number of articles read by participants; “Track” interactions are defined as the number of times a participant registered or viewed weight readings; “Support” interactions are defined as the number of messages sent or read in either the private or group chat channels.

#### **9.5.2. Control group**

Participants randomised to the control group will receive no additional intervention, and will continue to receive their usual NHS diabetes care from their general practice.

### **9.6. Subsequent Visits**

All Participants will be followed up after 3 months (visit 2) and at 12 months (visit 3).

They will be sent a reminder (initially via email or text, followed up by post and/or telephone call if required) to inform them to expect contact from their GP practice to book study appointments at both 3 and 12 months. These appointments are both study research visits. The appointments will take approximately 15 minutes. At this appointment they will have the same procedures as at their baseline assessment repeated: their weight and blood pressure will be recorded, and blood tests taken (3 sample tubes – for HbA1c, lipid profile and liver function). These visits will be combined with routine clinical care visits where possible. We will explicitly gain consent from participants to be able to extract relevant outcome measure data from their medical records during this time period matching that which would have been collected at the face-to-face appointments (blood results, weight, blood pressure) (which may be used, for example, if a patient is unable to attend their scheduled follow up appointment but has not withdrawn from the study and has attended their practice for relevant measurements in the interim).

They will also be asked to complete the same online questionnaires (PAID score, EQ5D, and 24 hour dietary recall) as they completed at baseline, again at 3 and 12 months, with the addition of specific questions to proactively ascertain any SAEs which may have occurred (and demographic information will not be re-requested as this is not presumed to have changed).

A purposively sampled proportion of participants from the intervention group (aiming to achieve diversity of age, race, and success and engagement with the programme measured by weight/HbA1c outcomes and engagement metrics respectively) will be contacted via telephone for a semi-structured interview to discuss their experience of the intervention, after they complete the 3 month intervention period. Interviews will last approximately 30 minutes. With participants consent this will be audio-recorded.

After 12 weeks the active intervention period will be complete, but participants will retain access to the app interface with stored educational information they have been provided with, and hard copy accompanying information, to refer back to if they wish.

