### **10.2. Reporting Procedures for Serious Adverse Events**

The duration of the SAE recording period for each participant lasts from their enrolment on to the study, to their completion of the study. Any serious adverse event (SAE) occurring to a participant will be recorded at the time that the research team is made aware of the incident, and reported to the REC that gave a favourable opinion of the study where in the opinion of the clinically qualified Chief Investigator the event was 'related' (resulted from administration of any of the research procedures) and 'unexpected' in relation to those procedures. Reports of related and unexpected SAEs will be submitted within 15 working days of the Chief Investigator becoming aware of the event, using the HRA report of serious adverse event form, in accordance with HRA process. We will also proactively ascertain for any additional SAEs at the 3 and 12 month outcome data collection timepoints.

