### **11.2. Sample Size Determination**

Based on previous studies of this intervention(5) and studies in similar populations(3), we estimate an 8-10mmol/mol change in HbA1c at 12 months in the intervention group in those who engage with the programme (SD 8.6mmol/mol), with a 1-2mmol/mol (SD 6mmol/mol) change in the control group. With  $\alpha$  and  $\beta$  set at 0.05 this would require approximately 48 participants; however to power for a co-primary outcome would require 72 to 88 participants in total (allowing for variability in estimated effect size). In similar trials of behavioural interventions we would expect retention to follow up of >80%; allowing for the online nature of this trial, and the retention rates of observational studies of this intervention we will aim to recruit 100 participants to allow for cumulative attrition at the intervention sign-up, engagement, and follow up stages.

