### **12.2. Data Recording and Record Keeping**

The trial is being run with support from the PC-CTU. The data management will be run in accordance with the Trials Unit SOPs, which are fully compliant with Good Clinical Practice (GCP). A trial specific Data Management Plan (DMP) will be developed for the trial outlining in detail the procedures that will be put in place to ensure that high-quality data are produced for statistical analysis.

A unique trial specific number and/or code in any database will identify the participants. All data will be directly entered online by the participant unless followed- up by the research team, using phone calls,

text messages or email. There will be two databases as all information is collected online and therefore identifiable information is also collected. Only the trial team will be able to have access to the databases. Trial data will be kept in compliance with the relevant Sponsor's policy, in particular: the University of Oxford: Data Protection Checklist: <https://researchsupport.admin.ox.ac.uk/policy/data/checklist> and Practical: Consideration: <https://researchsupport.admin.ox.ac.uk/policy/data/practical>

The data will be stored in Sentry and REDCAP and both are held on University secure servers and the University IT team provide security through Firewalls and backups of the systems are taken daily.

The trial management file and any paper CRFs (if used) will be secured in a locked cabinet in a locked room in the Department of Primary Care Health Sciences.

On completion of the trial and data cleaning, the trial documentation will be transferred to a secure, GCP compliant archiving facility, where they will be held for five years. Participants' identifiable information will be destroyed at the end of the trial. Prior to database lock, the Data Manager will undertake a dataset review. The anonymised dataset will be stored on a University secure server with access held by the Senior Data Manager. Procedures in relation to data transfer are documented within the PC-CTU\_SOP\_DM108 and in accordance with the Information Governance Policy.

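### The plan names no source of serious adverse events that is independent of participant response, so deaths and admissions among non-responders may be missed

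*Combined protocol and SAP*

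**What the plan says.** - **Recording window.** Under Section 10.2 the SAE period for each participant "lasts from their enrolment on to the study, to their completion of the study", which the synopsis puts at 12 months.
- **Active route.** Section 10.2 promises: "We will also proactively ascertain for any additional SAEs at the 3 and 12 month outcome data collection timepoints". It names no source. Section 9.6 supplies the mechanism: the online questionnaires used at baseline are repeated "with the addition of specific questions to proactively ascertain any SAEs which may have occurred". Appendix B agrees, placing SAE reporting in the online questionnaire row.
- **Practice visits.** At 3 and 12 months "their weight and blood pressure will be recorded, and blood tests taken". No SAE enquiry is listed.
- **Passive route.** Any other SAE "will be recorded at the time that the research team is made aware of the incident" (Section 10.2). No section says who is to inform the team.
- **Medical records.** Section 9.6 seeks consent to extract outcome data "matching that which would have been collected at the face-to-face appointments (blood results, weight, blood pressure". Admissions and deaths are not on the list.
- **Team follow-up.** Section 12.2 says that data are "entered online by the participant unless followed- up by the research team, using phone calls", texts or email. It does not mention SAEs.
- **Retention.** For similar behavioural trials, Section 11.2 states that "we would expect retention to follow up of >80" per cent.

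**The concern.** A questionnaire cannot be answered by someone who has died, and may not be answered by someone who is in hospital, seriously ill or no longer engaged. These are the people in whom an SAE is most plausible. Section 9.8 adds a related group: participants may stop treatment or assessments, for example because of an adverse event they find intolerable, and still remain in follow-up. They may return no questionnaire even though their records stay available.

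Section 10 sets up collection of SAEs and of no other adverse events, so these are the trial's only systematic harms data. Two things depend on them. One is any SAE summary in the trial report. The other is expedited reporting: the 15-working-day clock for related and unexpected events starts when the Chief Investigator becomes aware. An event soon after the 3-month questionnaire might first surface about 9 months later, or not at all. Section 13 provides no separate data monitoring committee, and the Trial Management Group can oversee only what reaches it.

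**Working it through.** The plan gives no SAE rate, capture rate or safety power, so there is no stated figure to reproduce. The check is a comparison of the routes, followed by an illustration.

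**1. Which routes work when the participant does not respond**

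| Route | Section | Needs the participant? | Can find a death? |
|---|---|---|---|
| Online SAE questions, 3 and 12 months | 9.6, Appendix B | Yes | No |
| Team phone, text or email follow-up | 12.2 | Yes, as described | Not by design |
| Team made aware | 10.2 | Not necessarily, but no reporter is named | Only if someone volunteers it |
| Record extraction | 9.6 | No | Not among the listed items |

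The one route that does not need the participant is the one whose scope leaves SAEs out.

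**2. Share of SAEs that the questionnaire alone would miss**

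Let n be the proportion not responding and r the SAE risk in non-responders relative to responders. Then

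missed share = n·r / [(1 − n) + n·r].

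Take n = 0.20, from the retention floor in Section 11.2 used as a proxy for questionnaire response. The values of r are assumptions.

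- r = 1: 0.20 / (0.80 + 0.20) = 20%
- r = 2: 0.40 / (0.80 + 0.40) = 33%
- r = 3: 0.60 / (0.80 + 0.60) = 43%

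The responders' base rate cancels. In counts, with 100 participants and an assumed 10% risk in responders, 80 × 10% = 8 events are seen. Of the 20 non-responders, 20 × 10% = 2 (r = 1) or 20 × 20% = 4 (r = 2) have events that are not seen: 2/10 = 20% and 4/12 = 33%.

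**3. How far this moves**

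- *Worse response.* In the service evaluation described in Section 5, 65.3% of starters gave a 12-month weight, so n = 0.347. The shares become 34.7% (r = 1) and 0.694/1.347 = 51.5% (r = 2). This is a pessimistic bound, not a forecast.
- *Answered at 3 months but not at 12.* With a constant event rate, only 9/12 of these people's events are exposed: 20% × 0.75 = 15% and 33.3% × 0.75 = 25%.
- *Half of non-responders' events recovered by other routes* (assumed): 20% × 0.5 = 10% and 33.3% × 0.5 = 17%.

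**4. Between arms**

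Let s₁ and s₀ be the fractions of non-responders' SAEs captured by other routes in the intervention and control arms. With no true difference and equal non-response,

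apparent ratio = [(1 − n) + n·r·s₁] / [(1 − n) + n·r·s₀].

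For n = 0.20 and r = 1:

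- s₁ = 0.75, s₀ = 0.25: 0.95/0.85 = 1.12
- s₁ = s₀: 1.00
- s₁ = 0.25, s₀ = 0.75: 0.85/0.95 = 0.89

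The sign depends entirely on s₁ and s₀, about which the plan says nothing.

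**The case against.** The best defence is that the plan is not closed to other sources. Section 10.2 records any SAE that the team learns of and does not restrict its proactive check to self-completion. Section 12.2 allows staff to chase data, Section 9.6 provides visit reminders by post and telephone, Section 9.8 has the team speak with people who leave treatment, and Section 16.7 offers a voucher for 12-month data. The trial is described as low risk, has a steering committee, lists no safety outcome and plans no SAE comparison. The consent form, Data Management Plan and trials unit SOPs are not part of the document reviewed and may say more.

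Much of this stands, and it rules out several stronger readings that a reader might infer:

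- *That SAEs are sought only by self-completed questionnaire, or that events in non-responders are certain to be missed.* The documents support the only *specified active* route, and events that *may* be missed.
- *That record extraction rescues efficacy data for the same people whose SAEs are lost.* The example in Section 9.6 is someone who missed a study visit but had measurements taken at the practice in the meantime. Someone who has died or disengaged is a different case.
- *That spontaneous reporting biases the comparison between arms.* The intervention arm does have coaching, an extra GP or nurse call and, for a sample, an interview. However, no route is stated from coach or practice to the research team for SAEs. If extra contact did raise reporting, it would more likely make the intervention look less safe.
- *That the percentages estimate the actual loss.* Retention and weight submission are stand-ins for questionnaire response, and r is assumed.

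What the defence does not supply is a named source that works without the participant.

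**Conclusion.** The point holds as a gap in specification. The active check rests on participant self-report at 3 and 12 months, record extraction does not list admissions or deaths, and nobody is assigned to notify the team. Following the plan as written could leave deaths and admissions in non-responders unrecorded.

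The size is illustrative: 20% to 33% of SAEs missed by the questionnaire alone, assuming 20% non-response, a one- to two-fold risk in non-responders and no recovery elsewhere. Recovery, or an answer at 3 months, lowers these figures; poorer response raises them. Differential ascertainment by arm is possible, unproven and of uncertain direction.

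The primary HbA1c analysis and the sample size are unaffected. What would lack support is a comparative statement about SAEs in the report. This is a cheap improvement, not a flaw that undermines the trial.

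**What to change.** In Sections 9.6 and 10.2, and in the consent and CRF wording:

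- Extend record extraction to hospital admissions and deaths, from enrolment (to match the window in Section 10.2) to 12 months.
- Apply it identically in both arms to every randomised participant who has not withdrawn consent, including those who stop treatment or miss questionnaires.
- Collect it when the practice record is opened for the 12-month results, and state that the record is opened even when there are no 12-month results to supply.
- Use it as the common source for any SAE summary by arm, with self-reports and spontaneous reports added.

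Section 9.7 already takes blood results from medical records onto the CRF, so the access route exists. The cost is a change of consent wording and a modest review for about 100 participants at about 10 practices. Finding admissions means reading entries and correspondence, which is more work than copying a laboratory value. No new visit or change in sample size is needed.
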